### **7 Sample Size Justification**

A sample size of 100 subjects was planned for enrollment in this study. No formal hypothesis was being tested in this study, thus the sample size was not statistically sized, but rather was considered sufficient for a descriptive summary of performance endpoints within each procedure group. It was expected that at least 2 vessels would be transected within each procedure, providing an expected minimum of at least 60 transections within colectomy and gynecological procedure groups and at least 40 transections in the thoracic procedure group for a total of at least 200 transections across all procedures.

From a safety perspective on the pooled analysis of 100 subjects and in consideration of rare adverse events (AEs) that may occur (e.g., bleeding requiring blood product transfusion), for an event that has an incidence rate of, for example, 2%, then in a sample of 100 subjects, the probability of observing at least 1 event is 86.7% under a binomial probability model. Thus, this sample size provides a high probability of observing rare events if they do occur, and provides reasonable assurance to conclude that the likelihood of such AEs is less than 3.7% if they do not occur based on the upper limit of an exact 95% confidence interval when 0 events out of 100 subjects are observed.

## **8 Analyses to be Conducted**

### **8.1 General Conventions**

Subject data will be summarized in tables and presented in further detail in listings. All eCRF data will be listed per subject for all subjects. Descriptive statistical analyses will be provided for pre-specified study endpoints. Summaries for continuous variables will include a minimum of number of observations (n), mean, standard deviation, median, minimum, and maximum. Summaries for categorical variables will include number and percentage.

Analyses will be conducted using SAS software. During the course of programming of tables that are mocked up in this SAP, minor modifications may become necessary. Examples of these minor modifications include, but are not limited to, re-wording of a footnote, addition of a footnote, re-labeling of a column, or addition or removal of a column from a listing. In cases where modifications to tables or listings are not related to a change in statistical analysis methodology or conclusions that could be made on the originally proposed methodology, then no amendment of the SAP is necessary. Any final analyses that differ from what has been specified in this document will be identified within the final statistical output and documented within the clinical study report.

### **8.2 Disposition of Study Subjects**

Subject disposition will be summarized by procedure group (colectomy, gynecological, and thoracic) and in total using counts and percentages. The number and percentage of subjects in the ENSEAL Analysis Set who completed and discontinued will be tabulated along with the specific reasons for discontinuation.

### **8.3 Demographic, Baseline, and Surgical Characteristics**

Summary statistics of subject demographics (age, gender, childbearing potential, race, and ethnicity) will be presented by procedure group and in total. Vital signs (height, weight, and body mass index) and background information (primary indication, specific procedure performed, gravidity, parity, smoking history, and cancer history) will be summarized in a similar manner. Medical history will be summarized by Medical Dictionary for Regulatory Activities (MedDRA) system organ class and preferred term. Surgical characteristics including, at minimum, procedure duration, occurrence of vessel skeletonization, presence of inflamed tissue or calcified

tissues/vessels, volume of estimated intra-operative blood loss, and use of ENSEAL X1 for tissue cutting or dissection will be summarized by procedure group and in total.

## 8.4 Primary and Secondary Endpoints and Associated Hypotheses

### 8.4.1 Primary Endpoint and Associated Hypotheses

No formal hypotheses are specified for this study. The study endpoints are representative of endpoints that are currently reported in the available literature for similar energy devices and this will allow for qualitative comparisons with the results from this study.

The primary performance endpoint in this study is the percentage of vessels where hemostasis ( $\leq$  Grade 3) is achieved using the ENSEAL X1 device and no additional hemostatic products (e.g., hemoclips, staples, sutures, fibrin sealants, other advanced energy) are needed to obtain hemostasis. The hemostasis grading scale applied is defined as:

- Grade 1: no bleeding at transection site;
- Grade 2: minor bleeding at transection site, no intervention needed;
- Grade 3: minor bleeding at transection site, mild intervention needed, use of monopolar device and/or touch-ups with ENSEAL X1;
- Grade 4: significant bleeding (e.g., pulsatile blood flow, venous pooling) requiring intervention such as extensive coagulation or ligation with additional hemostatic products (e.g., hemoclips, staples, sutures, fibrin sealants, other advanced energy products).

The primary performance endpoint will be summarized at the transection level as multiple transections per subject are expected; that is, the denominator for the primary endpoint will be the total number of transections and the numerator will be the number of transections where hemostasis ( $\leq$  Grade 3) was achieved. An exact 95% confidence interval using the Clopper-Pearson method will also be estimated. Primary performance endpoint summaries will be provided for each procedure group and in total.

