### **5 Levels of Significance**

No hypotheses are specified for this study and no p-values are being calculated, therefore no level of significance is specified. All estimation of endpoints will be performed using 95% confidence intervals.

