### 8.8 Sensitivity Analyses

The analysis of the primary performance endpoint described above in Section 8.4.1 makes the assumption of independence of transections within a subject in estimation of variance for the confidence interval calculation. To account for the potential dependence among transections within a subject, a sensitivity analysis will be performed where the 95% confidence interval will be estimated using a bootstrap approach. For each subject, the outcome of all transections will be represented by a vector of 1’s (indicating a score of  $\leq$  Grade 3 hemostasis) and 0’s (indicating a score of Grade 4 hemostasis). This vector will be re-sampled with replacement to generate a bootstrap sampled vector of observations for each subject. Then, the proportion of observations

scored as  $\leq$  Grade 3 hemostasis for each subject will be calculated from this bootstrap vector. After obtaining a sample proportion of transections achieving  $\leq$  Grade 3 hemostasis for each subject, the mean of these sample proportions will be calculated across all subjects to provide an estimated sample proportion of transections achieving  $\leq$  Grade 3 hemostasis based on 1 iteration of the bootstrap process. This process will then be repeated a minimum of 5000 times to generate a sampling distribution for the proportion of transections achieving  $\leq$  Grade 3 hemostasis. The mean of this sampling distribution will be provided as the point estimate of the proportion of transections achieving  $\leq$  Grade 3 hemostasis and the 95% confidence interval will be estimated by the lower 0.025 and upper 0.975 percentiles of this sampling distribution.

The table below demonstrates 1 iteration of this bootstrap process.

Subject ID	Observed Data Vector	Bootstrap Sampled Vector	Bootstrap-Based Sample Proportion
1	(1, 1, 0, 1, 1)	(1, 0, 1, 0, 1)	0.60
2	(1, 1, 1)	(1, 1, 1)	1.0
3	(1, 0, 1, 1)	(0, 1, 1, 1)	0.75
4	(1, 1, 0, 1, 1)	(1, 1, 1, 1, 1)	1.0
5	(1, 1)	(1, 1)	1.0
...	...	...	...
...	...	...	...
N	(0, 1, 1, 0, 1)	(1, 0, 1, 1, 1)	0.80
Summary			Mean of above proportions to get 1 observation in the sampling distribution of the proportion of transections achieving $\leq$ Grade 3 hemostasis.

The above re-sampling process will then be repeated a minimum of 5000 times to estimate the sampling distribution.

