Characteristic	Colectomy (N = ##)	Gynecological (N = ##)	Thoracic (N = ##)	Total (N = ##)
Occurrence of Vessel Skeletonization?				
Yes	xx (xx.x%)	xx (xx.x%)	xx (xx.x%)	xx (xx.x%)
No	xx (xx.x%)	xx (xx.x%)	xx (xx.x%)	xx (xx.x%)
Presence of Inflamed Tissue or Calcified Tissues/Vessels				
Yes	xx (xx.x%)	xx (xx.x%)	xx (xx.x%)	xx (xx.x%)
No	xx (xx.x%)	xx (xx.x%)	xx (xx.x%)	xx (xx.x%)
Was ENSEAL X1 Used for Tissue Cutting or Dissection?				
Yes	xx (xx.x%)	xx (xx.x%)	xx (xx.x%)	xx (xx.x%)
No	xx (xx.x%)	xx (xx.x%)	xx (xx.x%)	xx (xx.x%)
Procedure Duration (hours)				
n	xx	xx	xx	xx
Mean (SD)	xx.x (xx.x)	xx.x (xx.x)	xx.x (xx.x)	xx.x (xx.x)
Median (Min, Max)	xx.x (xx, xx)	xx.x (xx, xx)	xx.x (xx, xx)	xx.x (xx, xx)
Volume of Estimated Intra-operative Blood Loss (mL)				
n	xx	xx	xx	xx
Mean (SD)	xx.x (xx.x)	xx.x (xx.x)	xx.x (xx.x)	xx.x (xx.x)
Median (Min, Max)	xx.x (xx, xx)	xx.x (xx, xx)	xx.x (xx, xx)	xx.x (xx, xx)
Uterine Size (grams)				
n		xx		
Mean (SD)		xx.x (xx.x)		
Median (Min, Max)		xx.x (xx, xx)		

Table 7  
Vessel Transection Summary – Original Procedure  
ENSEAL Analysis Set

Characteristic	Colectomy (N = ##)	Gynecological (N = ##)	Thoracic (N = ##)	Total (N = ##)
Total Number of Vessels Transected	xx	xx	xx	xx
Hemostasis Grading Scale				
Grade 1	xx (xx.x%)	xx (xx.x%)	xx (xx.x%)	xx (xx.x%)
Grade 2	xx (xx.x%)	xx (xx.x%)	xx (xx.x%)	xx (xx.x%)
Grade 3	xx (xx.x%)	xx (xx.x%)	xx (xx.x%)	xx (xx.x%)
Grade 4	xx (xx.x%)	xx (xx.x%)	xx (xx.x%)	xx (xx.x%)
Hemostasis Achieved (Grade 3 or lower)				
Yes, n (%)	xx (xx.x%)	xx (xx.x%)	xx (xx.x%)	xx (xx.x%)
95% Confidence Interval	xx.x%, xx.x%	xx.x%, xx.x%	xx.x%, xx.x%	xx.x%, xx.x%
Tissue Stick Score, n (%)				
1 - No sticking	xx (xx.x%)	xx (xx.x%)	xx (xx.x%)	xx (xx.x%)
2 - Slight sticking	xx (xx.x%)	xx (xx.x%)	xx (xx.x%)	xx (xx.x%)
3 - Sticking requiring counter tension	xx (xx.x%)	xx (xx.x%)	xx (xx.x%)	xx (xx.x%)
4 - Sticking requiring extensive force	xx (xx.x%)	xx (xx.x%)	xx (xx.x%)	xx (xx.x%)
Number of Grade 3 Vessels Using Compression	xx	xx	xx	xx
Number of Grade 3 Vessels Using Monopolar Touch-up	xx	xx	xx	xx
Number of Monopolar Touch-ups				
n	xx	xx	xx	xx
Mean (SD)	xx.x (xx.x)	xx.x (xx.x)	xx.x (xx.x)	xx.x (xx.x)
Median (Min, Max)	xx.x (xx, xx)	xx.x (xx, xx)	xx.x (xx, xx)	xx.x (xx, xx)
Number of Grade 3 Vessels Using ENSEAL X1 Touch-up	xx	xx	xx	xx
Number of ENSEAL X1 Touch-ups				
n	xx	xx	xx	xx
Mean (SD)	xx.x (xx.x)	xx.x (xx.x)	xx.x (xx.x)	xx.x (xx.x)
Median (Min, Max)	xx.x (xx, xx)	xx.x (xx, xx)	xx.x (xx, xx)	xx.x (xx, xx)

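### The primary-endpoint Clopper-Pearson interval treats transections within a subject as independent, so its 95% coverage is not assured, and the SAP 8.8 bootstrap does not repair this

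*SAP*

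**What the plan says.** SAP 8.4.1 says the primary endpoint is "summarized at the transection level as multiple transections per subject are expected", and that "the denominator for the primary endpoint will be the total number of transections". The interval sentence follows: "An exact 95% confidence interval using the Clopper-Pearson method will also be estimated". Results are to be given for each procedure group and in total.

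SAP 8.8 acknowledges that this analysis "makes the assumption of independence of transections within a subject in estimation of variance for the confidence interval calculation". Its response is that "a sensitivity analysis will be performed where the 95% confidence interval will be estimated using a bootstrap approach". The resampling unit is the transection within the subject: "This vector will be re-sampled with replacement to generate a bootstrap sampled vector of observations for each subject". Subject proportions are then averaged without weights, and the step is repeated at least 5000 times.

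In the SAP appendix, the Table 7 block that begins "Hemostasis Achieved (Grade 3 or lower" has one confidence-interval row. The shell names no method; that comes from 8.4.1. Tables 8 to 10.8 reuse the format. The appendix says that shells are given for all summaries, but none holds the bootstrap interval.

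SAP 5 rules out hypotheses and p-values and adds: "All estimation of endpoints will be performed using 95% confidence intervals".

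**The concern.** Transections in one subject share tissue, vessel condition, coagulation state and usually the operator, so their outcomes are likely to be positively correlated. A binomial interval on the transection count then uses more information than the data hold. The exact method guarantees coverage only for independent trials.

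No test is planned, so the interval is the plan's statement of uncertainty about the primary endpoint. SAP 8.4.1 expects readers to set the results beside published rates for similar devices. An interval with less than its stated coverage would make that comparison look firmer than it is.

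**Working it through.** **The plan's own figures.** 30 × 2 = 60, 20 × 2 = 40 and 100 × 2 = 200 transections reproduce the stated minimums (Protocol 4.5.7, SAP 7). The safety figures also reproduce: 1 − 0.98^100 = 86.7%, and 1 − 0.025^(1/100) = 3.62%, below the stated 3.7%. No width or coverage is stated for the primary interval.

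**Inputs.** From the documents: 95% two-sided level, Clopper-Pearson on transections, 100 subjects, group minimums of 30, 30 and 20, and at least 2 transections per subject. The illustrative vectors in SAP 8.8 have 2 to 5. Assumed: ICC 0 to 0.3, true success rate 90 to 98%, and equal numbers of transections per subject (m) from 2 to 8. The only hint about the rate is SAP 8.4.2, which reports few Grade 4 ratings.

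**Design effect.** Effective n = total / (1 + (m − 1) × ICC). With 95% observed success and ICC 0.2:
- 30 × 4: 120 / (1 + 3 × 0.2) = 75. The Clopper-Pearson lower limit moves from 89.4% to 87.4%.
- 20 × 8: 160 / (1 + 7 × 0.2) = 66.7. The lower limit moves from 90.4% to 86.7%.

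**Coverage (%) of the planned interval.** Beta-binomial simulation with 20,000 trials per cell, except the two rows marked *, which used 2,000. Separate runs agreed to within about 1 point.

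| Subjects × m | True rate | ICC 0 | ICC 0.1 | ICC 0.2 | ICC 0.3 |
|---|---|---|---|---|---|
| 30 × 2 | 95% | 99.0 | 98.7 | 98.2 | 97.9 |
| 20 × 2 | 95% | 98.5 | 98.1 | 97.6 | 97.1 |
| 30 × 2 | 90% | 97.1 | 96.3 | 95.7 | 94.3 |
| 20 × 2 | 90% | 97.0 | 96.1 | 94.9 | 94.5 |
| 100 × 2 | 95% | 96.8 | 95.8 | 94.5 | 93.9 |
| 30 × 4 | 95% | 96.6 | 93.9 | 91.0 | 87.7 |
| 30 × 4 * | 97% | – | 97.5 | 96.5 | 95.1 |
| 30 × 4 * | 98% | – | 97.3 | 96.5 | 95.4 |
| 100 × 4 | 95 to 97% | – | about 93 | about 90 | about 87 |
| 100 × 5 | 95% | 96.3 | 91.8 | 87.8 | 83.8 |
| 20 × 8 | 95% | 97.7 | 91.1 | 84.8 | 78.2 |
| 20 × 8 | 98% | 98.4 | 94.9 | 92.3 | 89.9 |

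The exact interval is conservative in small samples, and that reserve absorbs mild clustering. It runs out as m, the ICC or the number of subjects grows.

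**Does 8.8 repair it?** No. Every subject appears once in every bootstrap sample, so variation between subjects, which is what clustering adds, never enters. A subject with all successes always returns 1.0, like subjects 2 and 5 in the SAP's own table. For 100 subjects, m = 5, rate 90% and ICC 0.3, the widths are:
- Clopper-Pearson: 5.4 points (coverage 83 to 84%);
- SAP 8.8 bootstrap: 3.9 points (69%);
- bootstrap of whole subjects: 7.7 points (95%).

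The 8.8 interval was narrower than Clopper-Pearson in every simulated cell, so the check could reassure wrongly. It also estimates something else. In the six displayed rows, pooled success is 19/24 = 79.2%, while the mean of subject proportions is (0.80 + 1 + 0.75 + 0.80 + 1 + 0.60)/6 = 82.5%.

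**The case against.** The best case for the plan is that it states the independence assumption openly, adds a sensitivity analysis and tests nothing. At the only planned cluster size, 2 per subject, the group intervals hold their coverage if success is 95% or higher. With few Grade 4 ratings a high rate is plausible, and 30 × 4 then holds too. All of this stands except the reliance on the sensitivity analysis, which errs in the wrong direction. Two is also a planned minimum, and SAP 8.4.1 requires a pooled interval, where there is less reserve.

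Several stronger readings are tempting but not supported:
- *The interval is too narrow.* That needs an ICC and a cluster size that the documents do not give.
- *The lower limit will be overstated.* For 30 × 4 at 97 to 98% it never exceeded the true rate at any ICC up to 0.3. For 20 × 8 at 95% and ICC 0.3 it did so in 11.5% of trials, against a nominal 2.5%.
- *The bootstrap is planned only for the pooled data.* The words about all subjects describe the averaging within one iteration. Section 8.8 refers back to the 8.4.1 analysis, which is by group and in total. The missing table shell is a documentation gap.
- *A conclusion hangs on the lower limit.* SAP 8.4.1 promises qualitative comparison only, and there is no performance goal.

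It is also fair to say that clustering by subject does not cover clustering by surgeon or site, for which SAP 8.10 plans no adjustment.

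**Conclusion.** The point holds in conditional form. The main interval rests on an independence assumption that the SAP itself names, and 95% coverage is not assured once subjects contribute several correlated transections. For ICCs of 0.1 to 0.3 the shortfall is about 2 to 8 points for the pooled 100 × 4 (coverage 87 to 93%) and about 4 to 17 points for 20 × 8 at a 95% rate (78 to 91%). There is none for groups of 20 to 30 with 2 per subject at a rate of 95% or more, nor for 30 × 4 at 97 to 98%. At a 90% rate with 2 per subject, groups of 20 to 30 fall at most slightly below 95%.

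These sizes rest on assumed ICCs, success rates and equal cluster sizes. The structural part does not: the headline interval ignores clustering, and the planned check does not measure it.

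**What to change.** In SAP 8.4.1 and the Table 7 format (Tables 7 to 10.8):

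1. **Main interval:** by procedure group and in total, a subject-clustered interval, such as Clopper-Pearson on the effective sample size (Korn-Graubard), capped at the number of transections.
2. **Sensitivity interval:** print the independence-based Clopper-Pearson interval beside it. The within-subject bootstrap of 8.8 should not serve as the check on dependence.
3. **No Grade 4 in a group:** show the ordinary Clopper-Pearson interval, flagged as assuming independence. Do not switch to the number of subjects as the sample size, because a perfect result would then look worse than one failure. For 30 × 4 with no Grade 4 that rule gives 0.025^(1/30) = 88.4%. With one Grade 4, the clustered variance is (0.9667² + 29 × 0.0333²) × (30/29) / 120² = 6.944 × 10⁻⁵, so effective n is (119/120 × 1/120) / 6.944 × 10⁻⁵ = 119.0. The factor (1.980/2.045)² for degrees of freedom reduces it to about 111.5, and the lower limit is 95.2%. The ordinary interval for 120/120 starts at 0.025^(1/120) = 97.0%, which keeps the order right.
4. **In all cases:** add the proportion of subjects with every transection at Grade 3 or lower, with its exact interval. This needs no assumption about dependence within a subject.

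The cost is SAP wording, an extra table row or two and a short macro, with no new data. Intervals will be somewhat wider. With very few Grade 4 ratings the clustering is poorly estimated (one rating leaves effective n almost unchanged above), so the adjusted interval improves on the present one without guaranteeing 95% in the smallest groups. The subject-level rate is the safeguard there.

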### 8.4.2 Secondary Endpoints and Associated Hypotheses

Counts and percentages will be provided for the following endpoints:

- type and number of vessels transected;
- grading scale distribution for all vessels transected;
- tissue sticking score of vessel transection;
- number of times compression was used for Grade 3 interventions;
- number of times monopolar device touch-ups were required for Grade 3 interventions; and,
- number of times ENSEAL X1 touch-ups were required for Grade 3 interventions.

The protocol identifies an additional endpoint of ‘the number of times additional hemostatic product was required to obtain hemostasis for Grade 4 bleeding’. Given the low number of Grade 4 ratings that have been observed in the trial at the time of finalization of this SAP, no summaries will be performed for this endpoint, and only a data listing will be generated.

#### 8.4.3 Additional Endpoints

Counts and percentages will be provided for responses to the device procedure questionnaire as well as the surgeon questionnaire. Free-text fields from both eCRFs will be listed. The requirement for any blood transfusion and time of the transfusion will be summarized with counts and percentages. Summary statistics will be provided for length of stay. All protocol deviations recorded during the study will be classified as minor or major. Counts and percentages will be provided for the type of deviation, the rationale for the deviation, and classification (minor or major).

### 8.5 Safety Analyses

The primary safety endpoint in this study is the occurrence of device-related AEs. All device-related and procedure-related AEs reported during the study will be coded to MedDRA. Per study protocol, related AEs are those identified as having a relationship of unlikely, possible, probable, or causal. All reported AEs will be summarized by MedDRA system organ class and preferred term by procedure group and in total. Separate summaries will be provided for device-related and procedure-related AEs. Serious AEs will be summarized in a similar manner. All reported adverse events will be listed. Listings will also be provided for blood transfusion details, chest tube details, concomitant procedures, and concomitant medications.

### 8.6 Plans for Interim Analysis

No interim analyses were planned or performed for this study.

### 8.7 Handling of Missing Data

All summaries will be performed only on enrolled subjects and only observed data will be summarized. There will be no imputation of data for early terminated subjects or for missing data within the database.

### 8.8 Sensitivity Analyses

The analysis of the primary performance endpoint described above in Section 8.4.1 makes the assumption of independence of transections within a subject in estimation of variance for the confidence interval calculation. To account for the potential dependence among transections within a subject, a sensitivity analysis will be performed where the 95% confidence interval will be estimated using a bootstrap approach. For each subject, the outcome of all transections will be represented by a vector of 1’s (indicating a score of  $\leq$  Grade 3 hemostasis) and 0’s (indicating a score of Grade 4 hemostasis). This vector will be re-sampled with replacement to generate a bootstrap sampled vector of observations for each subject. Then, the proportion of observations

scored as  $\leq$  Grade 3 hemostasis for each subject will be calculated from this bootstrap vector. After obtaining a sample proportion of transections achieving  $\leq$  Grade 3 hemostasis for each subject, the mean of these sample proportions will be calculated across all subjects to provide an estimated sample proportion of transections achieving  $\leq$  Grade 3 hemostasis based on 1 iteration of the bootstrap process. This process will then be repeated a minimum of 5000 times to generate a sampling distribution for the proportion of transections achieving  $\leq$  Grade 3 hemostasis. The mean of this sampling distribution will be provided as the point estimate of the proportion of transections achieving  $\leq$  Grade 3 hemostasis and the 95% confidence interval will be estimated by the lower 0.025 and upper 0.975 percentiles of this sampling distribution.

The table below demonstrates 1 iteration of this bootstrap process.

Subject ID	Observed Data Vector	Bootstrap Sampled Vector	Bootstrap-Based Sample Proportion
1	(1, 1, 0, 1, 1)	(1, 0, 1, 0, 1)	0.60
2	(1, 1, 1)	(1, 1, 1)	1.0
3	(1, 0, 1, 1)	(0, 1, 1, 1)	0.75
4	(1, 1, 0, 1, 1)	(1, 1, 1, 1, 1)	1.0
5	(1, 1)	(1, 1)	1.0
...	...	...	...
...	...	...	...
N	(0, 1, 1, 0, 1)	(1, 0, 1, 1, 1)	0.80
Summary			Mean of above proportions to get 1 observation in the sampling distribution of the proportion of transections achieving $\leq$ Grade 3 hemostasis.

The above re-sampling process will then be repeated a minimum of 5000 times to estimate the sampling distribution.

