## 1.2 Study Design

This is a prospective, single-arm, multi-center evaluation designed to collect clinical data in a post-market setting for colectomy, gynecological, and thoracic procedures. Investigators will perform each procedure using the device in compliance with their standard surgical approach and the ENSEAL X1 IFU.

Each site will utilize consecutive screening and enrollment in an effort to generate a random and representative patient population sample. Subjects will be consented and screened anytime between the time of scheduling the procedure and hospital admission (this period will vary per subject but may occur over several dates within an 8-week period prior to surgery). Subjects will be considered enrolled at the time of the first attempted vessel transection using the ENSEAL X1 device during their procedure. Procedures will be performed per each institution's standard-of-care (SOC) that is specific for each procedure group (colectomy, gynecological, and thoracic). The last study visit will be at the post-op follow-up visit at approximately 4 weeks. Follow-up by phone for subjects is allowed when an on-site visit is not planned.

A total of 100 eligible subjects were planned to be enrolled with a minimum of 30 subjects enrolled for colectomy procedures (e.g., total colectomy, partial colectomy, hemicolectomy, proctocolectomy), a minimum of 30 subjects enrolled for gynecological procedures (e.g., hysterectomy), and a minimum of 20 subjects enrolled for thoracic procedures (e.g., esophagectomy). The remaining 20 subjects could be enrolled from any of the three procedure groups and enrollment will be competitive between procedure groups.

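### The SAP 8.8 bootstrap resamples only inside fixed subjects, so it omits between-subject variance and, in expectation, narrows as within-subject dependence grows

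*SAP*

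**What the plan says.** SAP 8.4.1 defines the primary endpoint at transection level: "the denominator for the primary endpoint will be the total number of transections". It attaches a Clopper-Pearson 95% interval and adds "Primary performance endpoint summaries will be provided for each procedure group and in total".

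SAP 8.8 acknowledges that this interval treats transections within a subject as independent, and gives the purpose of the bootstrap: "To account for the potential dependence among transections within a subject, a sensitivity analysis will be performed". The steps are:

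- Each subject's outcomes form a vector of 1s (Grade 3 or lower) and 0s (Grade 4).
- "This vector will be re-sampled with replacement to generate a bootstrap sampled vector of observations for each subject".
- A proportion is taken for each subject, and "the mean of these sample proportions will be calculated across all subjects to provide an estimated sample proportion of transections".
- This is repeated at least 5000 times, and the 2.5 and 97.5 percentiles form the interval.

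The worked table follows the text. Subjects 1 to N each appear once, only the entries inside each vector change, and the summary row reads "Mean of above proportions to get 1 observation in the sampling distribution of the proportion of transections".

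Neither document plans another interval that allows for clustering.

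**The concern.** Dependence within a subject means that a subject's transections tend to succeed or fail together. Across the study this appears as variation between subjects. A bootstrap that keeps the same subjects in every iteration cannot see that variation. SAP 1.2 describes consecutive enrolment "in an effort to generate a random and representative patient population sample", so the subjects are meant to stand for a wider population and their sampling variation belongs in the interval.

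The method also moves the wrong way. A subject whose transections are all successes, all failures, or only one in number adds no bootstrap variance. In the worked table, subjects 2 and 5 can only return 1.0. The more strongly outcomes cluster, the more subjects are of this kind and the narrower the interval becomes.

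This is the only planned check on the independence assumption. A reader who sees it agree with, or fall inside, the Clopper-Pearson interval would take independence to be harmless whether or not it is.

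There is a smaller, second mismatch: 8.8 averages subject proportions but labels the result a proportion of transections, whereas 8.4.1 pools transections.

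**Working it through.** **The SAP's own illustration.** The resampled vectors give 3/5 = 0.60, 1.0, 3/4 = 0.75, 1.0, 1.0 and 4/5 = 0.80, as printed. So the algorithm is as read above. The SAP gives no numeric width or variance for the bootstrap.

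**Variance.** Take N subjects, m transections each, true rate p and intraclass correlation rho. Let phat_i be subject i's observed proportion.

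- Bootstrap variance given the data: (1/N²) Σ phat_i(1-phat_i)/m.
- Var(phat_i) = p(1-p)[1+(m-1)rho]/m, so E[phat_i(1-phat_i)] = p(1-p) - Var(phat_i) = p(1-p)(m-1)(1-rho)/m.
- Expected bootstrap variance: p(1-p)(m-1)(1-rho)/(N m²).
- True variance of the estimate: p(1-p)[1+(m-1)rho]/(N m).
- Ratio: (m-1)(1-rho)/{m[1+(m-1)rho]}.

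Example, m=2 and rho=0.3: 1 x 0.7/(2 x 1.3) = 0.269, and the square root is 0.52.

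| SE ratio, bootstrap/true | rho 0 | 0.1 | 0.3 | 0.5 | 1 |
|---|---|---|---|---|---|
| m=2 (SAP 7 minimum) | 0.71 | 0.64 | 0.52 | 0.41 | 0 |
| m=5 (assumed) | 0.89 | 0.72 | 0.50 | 0.37 | 0 |

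Against the independence variance p(1-p)/(Nm), the expected bootstrap variance is (m-1)(1-rho)/m times as large. That is below 1 for every rho from 0 to 1, so on average the check cannot come out wider than the independence calculation.

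**Coverage and width.** N=100 and at least 2 per subject come from SAP 7; p=0.98, rho and the larger cluster size are assumptions. Cells show coverage (mean width in percentage points).

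| Case | rho | SAP bootstrap | Resampling subjects | Clopper-Pearson |
|---|---|---|---|---|
| 100 x 2, exact | 0 | 88.6% (2.54) | 90.4% (3.63) | 96.2% (4.38) |
| | 0.1 | 84.4% (2.38) | 89.5% (3.74) | 95.3% (4.37) |
| | 0.3 | 75.5% (2.02) | 87.2% (3.96) | 93.1% (4.34) |
| 100 x about 5, simulated | 0 | 87% (2.18) | 93% (2.40) | 96% (2.66) |
| | 0.1 | 79% (2.05) | 91% (2.82) | 92% (2.63) |
| | 0.3 | 64% (1.78) | 87% (3.46) | 83% (2.61) |

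The exact case sums over the numbers of subjects with one and two Grade 4 results. The simulation is beta-binomial with 1+Poisson(4) transections per subject, 4000 trials x 2000 draws (Monte Carlo standard error up to 0.8 points).

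At 100 x 2 the SAP interval is narrower than Clopper-Pearson in every outcome. At about 5 per subject it is narrower in 96%, 97% and 98% of trials at rho 0, 0.1 and 0.3, against 93%, 40% and 16% when subjects are resampled. So at rho=0.3, where Clopper-Pearson really is too narrow, the planned check almost always says otherwise.

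**One data set.** Assume 100 x 2 with six Grade 4 results. Clopper-Pearson is 93.6-98.9% however they fall.

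| Six failures spread over | SAP bootstrap | Resampling subjects |
|---|---|---|
| 6 subjects | 95.5-98.5% | 94.5-99.0% |
| 4 subjects | 96.0-98.0% | 93.5-99.5% |
| 3 subjects | 97.0-97.0% | 93.0-100% |

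**Averaged against pooled.** The six observed rows shown in the worked table give (4+3+3+4+2+3)/(5+3+4+5+2+5) = 19/24 = 79.2% pooled. The mean of 0.80, 1, 0.75, 0.80, 1 and 0.60 is 82.5%.

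**The case against.** Three objections carry some weight.

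First, the practical harm depends on figures that are not in the documents. The only stated cluster size is at least 2. At 100 x 2 and p=0.98, Clopper-Pearson still covers 93.1% to 96.2% for rho up to 0.3, and at 30 x 2 it covers about 98-99%. There, trusting independence would be roughly right even though the check is invalid. This stands as a limit on consequence. But 2 is a floor, and a check that cannot detect the problem is no check even where the problem is small.

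Second, resampling subjects is no cure when failures are rare, and SAP 8.4.2 says they are: "Given the low number of Grade 4 ratings that have been observed in the trial at the time of finalization of this SAP". For one group of 30 x 2 (exact, rho 0/0.1/0.3), coverage is:

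| p (assumed) | SAP bootstrap | Resampling subjects | Clopper-Pearson |
|---|---|---|---|
| 0.95 | 78.7/74.1/62.2% | 94.7/94.1/92.3% | 99.0/98.6/97.9% |
| 0.98 | 68.5/61.2/46.9% | 70.1/68.2/64.1% | 99.3/99.0/98.3% |

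At p=0.98 and rho=0 the gain is under 2 points. This is why the fix cannot rest on the bootstrap alone.

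Third, equal weighting of subjects is defensible in a sensitivity analysis, and the illustrative table has 5/24 = 21% failures, so the 79.2% against 82.5% gap overstates what few Grade 4 events would produce. That is fair: the averaging point is secondary.

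None of these answers the main point. The text and the table agree, so it cannot be put down to loose wording.

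**Conclusion.** The concern holds. As written, the SAP 8.8 interval omits between-subject variance, is too narrow on average even with no dependence, and shrinks in expectation by the factor (1-rho) as dependence grows. This direction follows from the algebra for equal cluster sizes; individual data sets can vary. The coverage figures rest on assumed rates, correlations and, in the larger case, an assumed cluster size of about 5.

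The effect is on reported precision only. The study is descriptive, tests no hypothesis and sets no success threshold, and the primary estimate and its Clopper-Pearson interval do not change. It should still be corrected, because estimation with 95% intervals is the study's whole inferential output and SAP 8.4.1 expects qualitative comparison with the literature.

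**What to change.** In SAP 8.8 and its example table:

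1. Resample whole subjects with replacement and keep all transections of each sampled subject.
2. In each iteration compute the pooled transection proportion of 8.4.1, and take the 2.5 and 97.5 percentiles.
3. Do this for each procedure group and in total, matching 8.4.1.
4. Beside it, always show Clopper-Pearson and the lower limit of an exact subject-level interval: subjects with no Grade 4 over subjects with at least one graded transection. State that denominator, because SAP 6 also admits subjects through tissue cutting or dissection alone. For 30 subjects x 2, the Clopper-Pearson and subject-level lower limits are 94.0% (60/60) and 88.4% (30/30) with no Grade 4, and 91.1% (59/60) and 82.8% (29/30) with one.
5. State the limits. With few Grade 4 events the subject bootstrap under-covers and is often narrower than Clopper-Pearson (97%, 84% and 64% of trials at 100 x 2, p=0.98, rho 0/0.1/0.3), so a narrower interval is not evidence that independence is conservative. With no Grade 4 events any percentile bootstrap has zero width. The subject-level limit is a conservative bound, not an estimate, and needs similar numbers of transections per subject.

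Reporting the bound in every case avoids a rule that switches on the data. The cost is SAP wording, a new example table and a few lines of SAS, with no new data. The downside is a usually wider interval that still under-covers when events are rare, and a bound that is conservative.
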